### 9.5.1.2 Efficacy Assessments

The primary endpoint (ORR), secondary endpoint (PFS), and exploratory endpoints (CBR, DCR, and DOR) will be evaluated by the investigator. In addition, ORR, PFS, CBR, DCR and DOR will be assessed by IIR. The OS status will be assessed throughout the study.

#### 9.5.1.2.1 TUMOR ASSESSMENTS

Tumor assessments will be performed using RECIST v1.1. Investigator-determined response assessments are to be performed at the site by appropriately qualified personnel at each time point and recorded on the appropriate CRFs. Copies of all tumor assessment scans will be sent to an imaging core laboratory specified by the sponsor for quality assessment and independent imaging review. Tumor assessments will be carried out following the guidelines provided by the imaging core laboratory. Historical scans performed within the Screening period that do not follow the guidelines completely may be used to demonstrate eligibility, as long as they meet minimum standards as separately defined by the imaging core laboratory.

Tumor assessments including a CT chest and CT or MRI of the abdomen and pelvis, and other areas of known or newly suspected disease should be performed prior to Baseline (between Day -28 to Day -2) and every 8 weeks (within the 8th week) from the date of first dose during the Treatment Phase. The same imaging modality and image-acquisition protocol (including use or nonuse of contrast, oral and IV) should be used consistently across all time points. A brain scan will be performed at Screening, and thereafter if clinically indicated. Bone scans using whole body bone MRI, m-technetium (m-Tc) based bone scans, or F sodium fluoride positron-emission tomography (Na-F PET) will be performed during the pretreatment phase to establish a baseline (a historical bone scan performed within 6 weeks before first dose is acceptable), every 24 weeks, and as clinically indicated. Lesions identified on bone scans should be followed with cross-sectional imaging.

In subjects with complete response (CR) based on body CT/MRI scans, bone scan and brain scan, assessment will be required at response confirmation. All objective responses must be confirmed at least 28 days following the initial achievement of response. Subjects going off study treatments without disease progression in the Treatment Phase will continue to undergo tumor assessments according to the above schedule until disease progression is documented or another anticancer therapy is initiated.

### 9.5.1.3 Pharmacokinetic, Pharmacodynamic, Pharmacogenomic, and Other Biomarker Assessments

#### 9.5.1.3.1 PHARMACOKINETIC ASSESSMENTS

Sparse PK samples will be collected from all subjects and will be analyzed using the population approach. A total of 12 samples (6 plasma samples for lenvatinib and 6 whole blood samples for everolimus) per subject will be obtained at the following time points: 2 to 8 hours postdose on C1D1, prior to dose on Cycle 1 Day 15 (C1D15), prior to dose and 2 to 8 hours postdose on Day 1 of Cycles 2 and 3. Actual time and date of PK blood collection as well as time of drug administration will be recorded on the appropriate page of the CRF.

Refer to the Laboratory Manual for the total blood volume to be collected along with instructions for processing, shipping and handling of the samples.

Lenvatinib in plasma and everolimus in blood will be quantified using validated high pressure liquid chromatography (HPLC)-tandem mass spectroscopy methods.

#### 9.5.1.3.2 PHARMACODYNAMIC, PHARMACOGENOMIC, AND OTHER BIOMARKER ASSESSMENTS

##### **Blood and Tissue Biomarkers**

Biomarker discovery and/or validation may be performed to identify blood or tumor biomarkers that may be useful to predict subject response to study drug, evaluation of response-related and/or safety-related outcomes as well as for potential use in diagnostic development. In addition, biomarkers identified in other clinical studies of study drug may also be assessed in samples collected from subjects enrolled in this study. The decision to perform exploratory biomarker analysis may be based on the clinical outcome of this study and/or the signals observed in other clinical studies or other information available at that time.

A blood sample for pharmacodynamic and exploratory biomarker analysis will be collected predose on Day -1 or C1D1, on C1D15, and on Day 1 of subsequent cycles (during Treatment Phase), and at the End of Treatment assessment. Blood samples from all consented subjects may undergo analyses including, but not limited to, global proteomic and/or enzyme-linked immunosorbent assay (ELISA)-based analyses or multiplex bead-based immunoassay in an effort to assess pharmacodynamic biomarkers.

##### **Pharmacogenomic (PG) Assessments**

Archived, fixed tumor tissue will be collected (if available) from all subjects for potential assessment of mutations and other genetic alterations or genes and/or proteins that may be important in the development and progression of cancer as well as in response to study drug treatment for potential use in diagnostic development. Appropriate technology/methodologies will be used based on the amount of tumor tissue available.

A blood sample for peripheral blood mononuclear cells (PBMC) and plasma isolation will be collected from consented subjects for potential analysis of cell free nucleic acid (cf-nucleic acid) analysis and exploratory immune cell analysis. Cell free nucleic acid isolated from plasma samples may be used to obtain circulating tumor DNA (ctDNA) and explore tumor genetic alterations such as mutations observed in archival tumor samples as well as those which develop during drug treatment. PBMCs may be used for immune cell profiling (eg. tumor infiltrating lymphocytes, T-cell repertoire, and immune cell types).

A blood sample will be collected for pharmacogenomics (PG) analysis (except where prohibited by regional or local laws). Variation in lenvatinib exposure or the occurrence of AEs observed in the study population may be evaluated by correlating single-nucleotide polymorphisms with PK, safety, or pharmacodynamic data. Genomic DNA extracted from blood samples may be used to confirm whether the DNA sequence variants observed in DNA

extracted from tumor material are limited to the tumor and for potential profiling of immune cells.

Data obtained will be used for research, to assist in developing safer and more effective treatments and will not be used to change the diagnosis of the subject or alter the therapy of the subject. The DNA will not be used to determine or predict risks for diseases that an individual subject does not currently have. Any sample or derivatives (DNA, RNA, and protein) may be stored for up to 15 years to assist in any research scientific questions related to lenvatinib, cancer and/or for potential diagnostic development.

Instructions for the processing, storage, and shipping of samples will be provided in the Laboratory Manual.

#### 9.5.1.4 Safety Assessments

General safety will be assessed by the monitoring and recording of all AEs and serious adverse events (SAEs), regular monitoring of hematology and blood chemistry, regular measurement of vital signs, ECG, and the performance of physical examinations (PE) and other safety assessments in line with local regulations governing a study of this nature.

Progression of nccRCC and signs and symptoms clearly related to the disease progression should not be captured as an AE. Disease progression is a study endpoint and should be captured in the CRF as per the guidelines for reporting disease progression.

In case of life-threatening bleeding, the investigator should discuss the case with the Eisai Medical Monitor, in addition to discontinuing lenvatinib per Table 2 for Grade 4 toxicity and treat the subject based on the institution's standard practice. Clinically significant bleeding will be considered as study-specific events and should always be considered as serious important medical events, which will be entered on the adverse event CRF and reported using the procedures for reporting SAEs, even if the study-specific event does not meet other serious criteria.

Safety assessments will consist of monitoring and recording all AEs, including all CTCAE v4.03 grades (for both increasing and decreasing severity) (Appendix 5), and SAEs; regular monitoring of hematology, blood chemistry, and urine values; periodic measurement of vital signs and ECGs; and performance of physical examinations as detailed in Table 5.

##### 9.5.1.4.1 ADVERSE EVENTS AND EVENTS ASSOCIATED WITH SPECIAL SITUATIONS

An adverse event (AE) is any untoward medical occurrence in a patient or clinical investigation subject administered an investigational product. An AE does not necessarily have a causal relationship with the medicinal product. For this study, the study drugs are lenvatinib and everolimus.

The criteria for identifying AEs in this study are:

- Any unfavorable and unintended sign (including an abnormal laboratory finding), symptom, or disease temporally associated with the use of an investigational product,

whether or not considered related to the investigational product (Note: Every sign or symptom should not be listed as a separate AE if the applicable disease [diagnosis] is being reported as an AE)

- Any new disease or exacerbation of an existing disease
- Any new disease or exacerbation of an existing disease. However, worsening of the primary disease should be captured under efficacy assessments as disease progression rather than as an AE.
- Any deterioration in nonprotocol-required measurements of a laboratory value or other clinical test (eg, ECG or x-ray) that results in symptoms, a change in treatment, or discontinuation of study drug
- Recurrence of an intermittent medical condition (eg, headache) not present pretreatment (Baseline)
- An abnormal laboratory test result should be considered an AE if the identified laboratory abnormality leads to any type of intervention, withdrawal of study drug, or withholding of study drug, whether prescribed in the protocol or not

All AEs observed during the study will be reported on the CRF. All AEs, regardless of relationship to study drug or procedure, should be collected beginning from the time the subject signs the study ICF through the last visit and for 28 days after the last dose of study treatment. Subjects who fail screening primarily due to AE(s) must have the AE(s) leading to screen failure reported on the Screening Disposition CRF. SAEs will be collected for 28 days after the last dose of study treatment.

Abnormal laboratory values should not be listed as separate AEs if they are considered to be part of the clinical syndrome that is being reported as an AE. It is the responsibility of the investigator to review all laboratory findings in all subjects and determine if they constitute an AE. Medical and scientific judgment should be exercised in deciding whether an isolated laboratory abnormality should be classified as an AE. Any laboratory abnormality considered to constitute an AE should be reported on the Adverse Event CRF.

Abnormal ECG (QTcF) results, if not otherwise considered part of a clinical symptom that is being reported as an AE, should be considered an AE if the QTcF interval is more than 450 ms and there is an increase of more than 60 ms from baseline. Any ECG abnormality that the investigator considers as an AE should be reported as such.

All AEs must be followed for 28 days after the subject's last dose, or until resolution, whichever comes first. All SAEs must be followed to resolution or, if resolution is unlikely, to stabilization.

**Every effort must be made by the investigator to categorize each AE according to its severity and its relationship to the study treatment.**

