### 9.3.2 Exclusion Criteria

Subjects who meet any of the following criteria will be excluded from this study:

1. Predominant clear cell RCC.
2. Prior anticancer chemotherapy or targeted therapy for advanced nccRCC.
3. Prior exposure to lenvatinib or mTOR inhibitor.
4. Known intolerance to lenvatinib, everolimus (or other rapamycin derivatives), or any of the excipients.
5. Major surgery performed within 3 weeks prior to the first dose of study drugs or scheduled for major surgery during the study.
6. Gastrointestinal malabsorption, gastrointestinal anastomosis, or any other condition that might affect the absorption of lenvatinib or everolimus.
7. Subjects having  $> 1 +$  proteinuria on urine dipstick testing will undergo 24 hour urine collection for quantitative assessment of proteinuria. Subjects with urine protein  $\geq 1$  g/24 hours will be ineligible.
8. Fasting total cholesterol  $>300$  mg/dL (or  $>7.75$  mmol/L) or fasting triglycerides level  $>2.5 \times$  ULN. NOTE: these subjects can be included after initiation or adjustment of lipid-lowering medication.
9. Uncontrolled diabetes as defined by fasting glucose  $> 1.5$  times the ULN. NOTE: In case this threshold is exceeded, these subjects can only be included after initiation or adjustment of glucose-lowering medication.
10. Known history of, or any evidence of, interstitial lung disease or active noninfectious pneumonitis.
11. Significant cardiovascular impairment: History of (a) congestive heart failure greater than New York Heart association (NYHA) (Appendix 4) Class II, (b) unstable angina, (c) myocardial infarction (d) stroke, or (e) cardiac arrhythmia associated with hemodynamic instability within 6 months of the first dose of study drugs.
12. Prolongation of QTcF interval to  $>480$  msec.
13. Known history of human immunodeficiency virus (HIV) positive.
14. Known active hepatitis B (eg, hepatitis B surface antigen [HBsAg] reactive) or hepatitis C (eg, hepatitis C virus [HCV] RNA detected).
15. Clinically significant hemoptysis or tumor bleeding within 2 weeks prior to the first dose of study drug.
16. Subjects with central nervous system (CNS) (eg, brain or leptomeningeal) metastases.
17. Other active malignancy (except definitively treated melanoma in-situ, basal or squamous cell carcinoma of the skin, or carcinoma in-situ of the cervix or bladder) within past 24 months.

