#### 9.5.1.4.6 ELECTROCARDIOGRAMS

Electrocardiograms will be obtained as designated in the Schedule of Procedures/Assessments (Table 5). Complete, standardized, 12-lead ECG recordings that permit all 12 leads to be displayed on a single page with an accompanying lead II rhythm strip below the customary  $3 \times 4$  lead format are to be used. In addition to a rhythm strip, a minimum of 3 full complexes should be recorded from each lead simultaneously. Subjects must be in the recumbent position for a period of 5 minutes prior to the ECG.

An ECG abnormality may meet the criteria of an AE as described in this protocol (see [Section 9.5.1.4.1](#)) and the CRF Completion Guidelines. In these instances, the AE corresponding to the ECG abnormality will be recorded on the Adverse Events CRF.

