- Archived, fixed tumor tissue will be collected (if available) and may be used in the future for potential assessment of genetic biomarkers. The decision to perform other biomarker assessments may be based on the clinical outcome of this study and/or the signals observed in other studies or other information available at that time.
- Collection of blood samples to obtain serum, peripheral blood mononuclear cells, and/or plasma to be used for cell-free nucleic acid, immune cell, and biomarker studies from subjects. Samples will be obtained predose on Day -1 or C1D1, C1D15, Day 1 of all subsequent cycles, and at the End of Treatment Visit.
- ECOG will be performed at the Screening and Baseline Visits, on C 2/D1, on Day 1 of every subsequent cycle thereafter, and at the End of Treatment Visit.
- Assessments will include vital signs (resting BP, HR, RR, and body temperature), weight, and height. Height will be measured at the Screening Visit only. Vital signs will be performed at Screening, Baseline, C1D8, C1D15, C2D1, C2D15, Day 1 of every cycle thereafter, all unscheduled visits, and at the End of Treatment Visit. Elevated BP (systolic BP  $\geq$ 140 mmHg or diastolic BP  $\geq$ 90 mmHg) should be confirmed by repeat measurements after 1 hour to obtain a mean value.

- k. Subjects with systolic BP  $\geq$  160 mmHg or diastolic BP  $\geq$  100 mmHg must have their BP monitored every 2 weeks (on Day 15 or more frequently as clinically indicated) until systolic BP has been  $\leq$  150 mmHg and diastolic BP has been  $\leq$  95 mmHg for 3 consecutive months. If a new event of systolic BP  $\geq$  160 mmHg or diastolic BP  $\geq$  100 mmHg occurs, the subject must resume the Day 15 evaluation until systolic BP has been  $\leq$  150 mmHg and diastolic BP has been  $\leq$  95 mmHg for 3 consecutive months.
- l. A comprehensive physical examination (including a neurological examination) will be performed at the Screening Visit, on Cycle 1/Day 15, on Day 1 of each subsequent cycle, and at the End of Treatment assessment. A symptom-directed physical examination will be performed on Baseline (Day -1) or on C1D1 prior to treatment, and at any time during the study, as clinically indicated.
- m. Single 12-lead ECG. Subjects must be in the recumbent position for a period of 5 minutes prior to the ECG.

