#### **9.7.1.8 Safety Analyses**

Safety, using the FAS, will be assessed by monitoring and recording of all AEs including all CTCAE grades, regular monitoring of hematology and clinical chemistry, urinalysis, regular measurement of vital signs, 12-lead ECGs, and performance of physical examinations.

Adverse events and other clinical safety data will be summarized descriptively in the FAS. The incidence of TEAEs, SAEs, drug-related AEs, and AEs leading to discontinuation will be summarized in tabulation. Hematology, serum chemistry, vital sign variables and ECG will be summarized descriptively for observed values, by grade and by change from Baseline by cycle. All AEs and lab parameters will be listed.

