##### **9.7.1.8.2 ADVERSE EVENTS**

The AE verbatim descriptions (investigator terms from the CRF) will be classified into standardized medical terminology using the Medical Dictionary for Regulatory Activities

(MedDRA). Adverse events will be coded to the MedDRA (Version 17 or higher) lower level term (LLT) closest to the verbatim term. The linked MedDRA preferred term (PT) and primary system organ class (SOC) are also captured in the database.

A treatment-emergent adverse event (TEAE) is defined as an AE that emerges during treatment, having been absent at pretreatment (Baseline) or

- Reemerges during treatment, having been present at pretreatment (Baseline) but stopped before treatment, or
- Worsens in severity during treatment relative to the pretreatment state, when the AE is continuous.

Only those AEs that are treatment-emergent will be included in summary tables. All AEs, treatment-emergent or otherwise, will be presented in subject data listings.

The TEAEs will be summarized. The incidence of TEAEs will be reported as the number (percentage) of subjects with TEAEs by SOC and PT. A subject will be counted only once within an SOC and PT, even if the subject experienced more than 1 TEAE within a specific SOC and PT. The number (percentage) of subjects with TEAEs will also be summarized by maximum severity (mild, moderate, or severe by highest CTCAE grade).

The number (percentage) of subjects with TEAEs will also be summarized by relationship to each study drug and combined (Yes [related] and No [not related]).

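### The only printed numeric QTcF adverse-event rule amounts to QTcF > max(450, baseline + 60), so subjects entering at 441–480 ms can exceed 500 ms without meeting it (minor)

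*Protocol*

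**What the plan says.** Section 9.5.1.4.1 gives one numeric criterion for QTcF. Unless the result already belongs to a clinical picture being reported, it is to be "considered an AE if the QTcF interval is more than 450 ms and there is an increase of more than 60 ms", the increase being counted against baseline. The next sentence adds a route without a number: "Any ECG abnormality that the investigator considers as an AE should be reported as such". The general criteria earlier in the same section begin with "Any unfavorable and unintended sign (including an abnormal laboratory finding", and section 9.5.1.4.6 notes that "An ECG abnormality may meet the criteria of an AE as described in this protocol" and in the CRF Completion Guidelines, which are not at hand.

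Entry is limited separately. Exclusion criterion 12 in section 9.3.2 reads "Prolongation of QTcF interval to $>480$ msec", so a value of exactly 480 ms is eligible.

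On reporting, section 9.7.1.8 states that "ECG will be summarized descriptively for observed values, by grade and by change from Baseline by cycle", and section 9.7.1.8.5 plans descriptive statistics by visit. For adverse events, section 9.7.1.8.2 says "Only those AEs that are treatment-emergent will be included in summary tables". Table 5, note m, specifies "Single 12-lead ECG" at each scheduled time. Table 5 places the pretreatment ECG at Screening and none at the Baseline visit, so in practice the screening ECG serves as baseline.

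**The concern.** A numeric criterion is there to make sites call the same ECG result an adverse event. This one works on change alone once the baseline reaches 390 ms: from there upward the 450 ms condition no longer decides anything, and no absolute ceiling remains. The value needed to meet the rule then rises one for one with baseline, so the rule is least demanding of investigators in the subjects whose intervals are longest to begin with.

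At stake is consistency of adverse-event capture across about 8 sites. The adverse-event tables can hold only what investigators report. Dose modification under Table 3 works from graded treatment-related toxicity, and neither that table nor sections 9.4.1.1.1 to 9.4.1.1.9 gives a QTcF limit of its own. Recognising a very long interval as an adverse event is therefore left to judgment for the subjects in whom a numeric backstop would be most useful.

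**Working it through.** **Inputs.** The rule (section 9.5.1.4.1): QTcF > 450 ms and QTcF − baseline > 60 ms. Eligible baselines (section 9.3.2, criterion 12): up to and including 480 ms. The protocol states no derived figure to reproduce.

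**Step 1: rewrite the rule.** With baseline b, QTcF − b > 60 is the same as QTcF > b + 60. Both conditions hold exactly when

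QTcF > T(b) = max(450, b + 60).

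Checking every whole-millisecond pair (b from 300 to 480, QTcF from 300 to 650) showed no disagreement between the two forms.

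**Step 2: put in baselines.** T(b) is the highest value that does not meet the rule.

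| Baseline (ms) | Highest unflagged now (ms) | With > 500 ms added (ms) |
|---|---|---|
| 390 | 450 | 450 |
| 391 | 451 | 451 |
| 420 | 480 | 480 |
| 440 | 500 | 500 |
| 441 | 501 | 500 |
| 450 | 510 | 500 |
| 460 | 520 | 500 |
| 480 | 540 | 500 |

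**Step 3: read off the range.** A value above 500 ms can go unflagged when b + 60 > 500, that is b > 440, so in whole milliseconds for eligible baselines of 441–480 ms. The maximum is 480 + 60 = 540 ms, reached only at a baseline of 480 ms.

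**Step 4: two subjects compared.**
- 391 to 452 ms: 452 > 450, and 452 − 391 = 61 > 60. The rule is met.
- 480 to 540 ms: 540 > 450, but 540 − 480 = 60, which is not more than 60. The rule is not met.

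**Step 5: how many more adverse events the added clause might bring.** The protocol gives no QTcF mean, spread or drug effect, so this is illustration only. Normal distributions were assumed for baseline (cut off at 480 ms) and for change, 1.5 million subjects were simulated per scenario, and results were scaled to 31. Seven ECGs means Cycle 1 Day 15, Day 1 of Cycles 2 to 6 and End of Treatment (1 + 5 + 1 = 7), all obtained in every subject, with the variance of change split equally between and within subjects. The last two columns count subjects with a value above 500 ms who never meet the present rule, before any repeat ECG.

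| Scenario | Baseline mean, SD (ms) | Change mean, SD (ms) | One ECG, per 31 | Seven ECGs, per 31 |
|---|---|---|---|---|
| A | 415, 20 | 10, 15 | 0.03 | 0.14 |
| B | 415, 20 | 15, 20 | 0.12 | 0.40 |
| C | 430, 20 | 15, 20 | 0.54 | 1.61 |
| D | 430, 20 | 20, 25 | 0.88 | 1.94 |

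**The case against.** The strongest reply is that the rule is a floor. It says when a QTcF result must be called an adverse event and does not say that other results are not. The sentence that follows it, and the general definition, leave the investigator free to report a value of 540 ms, and the unseen CRF Completion Guidelines may say more. This stands. A reader might infer that such results go unreported or vanish from the study, and the documents do not support that: judgment remains open, and ECGs are summarised by value, grade and change whether or not an adverse event is filed. What remains is that these routes carry no number.

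A reader might also infer that the rule contradicts the 480 ms entry limit. It does not. Criterion 12 decides who may enter, while the rule in section 9.5.1.4.1 looks for a change on treatment. Any rule that requires a change from baseline will tolerate higher values in those who start higher.

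The protocol adopts CTCAE v4.03 for grading, but grading applies to events already identified as adverse events, and Appendices 5 and 7 print no QTc cut-off. Calling this the only numeric rule is therefore a statement about the printed protocol, not about every study document.

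Finally, the simulated counts depend on chosen inputs. That also stands. Between scenarios they differ many-fold, and none of the inputs comes from the protocol.

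**Conclusion.** The point holds as a minor safety improvement. The equivalence to QTcF > max(450, baseline + 60), the 441–480 ms range and the 540 ms ceiling follow exactly from two printed criteria and need no assumption beyond taking the screening ECG, or any other value within the entry limit, as baseline. The stated rule obliges reporting of 391 to 452 ms and leaves 480 to 540 ms to discretion.

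It goes no further than that. There is no internal contradiction, no loss of ECG data, no effect on the response rate and no demonstrated effect on dosing. How many of the 31 subjects would be concerned is unknown; the illustrative range of about 0.03 to 1.9 newly flagged subjects shows only that the added clause would be a light burden under the distributions tried. The point is not one to leave to the statistical analysis plan, because what counts as an adverse event is an instruction to investigators.

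**What to change.** In section 9.5.1.4.1 keep the present QTcF rule and add an alternative: *or a postbaseline QTcF above 500 ms, confirmed on a repeat ECG*. The 500 ms level does not stand in the protocol; it is a proposal for the sponsor to confirm. Confirmation is sensible because each scheduled recording is single (Table 5, note m). The highest unflagged value then falls from 540 to 500 ms.

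Do not simply replace the *and* by *or* at 450 ms: a subject who enters at 451–480 ms and does not change would be flagged at once. The clause also deliberately leaves values of 481–500 ms with a rise of 60 ms or less to judgment. Flagging more of these would bring many more adverse events from single tracings.

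The cost is one clause and occasional repeat ECGs; the scheduled ECGs are already in place. The downside is a few additional ECG adverse events: on the assumed distributions and before confirmation, 0.03 to 0.9 subjects per 31 with one on-treatment ECG each, and 0.1 to 1.9 with seven.
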